8.2 SECONDARY ENDPOINT ANALYSES

The secondary efficacy outcome measures for this study are the following (the order is relevant to the sequence procedure for testing endpoints):

- Morphologic Complete Remission (CR) rate

- Transfusion independence
- CR_{M RD}- rate
- CR_c rate

A group-sequential procedure will be applied as described in section 5.5.

Morphologic Complete Remission (CR) rate

The rate of CR is defined as the proportion of patients who achieve a morphologic CR according to the IWG response criteria (Appendix F of the protocol) in the absence of interceding therapies, including salvage treatments and hematopoietic stem cell transplantation (HSCT), within the study period. Interceding therapies, salvage treatments, as well as HSCT are collected in the “New AML Treatment” eCRF page and in the concomitant medication page (if started before and continued into the treatment period or started during treatment period). The proportions in the two treatment groups will be compared using the Cochran-Mantel-Haenszel test stratified for cytogenetic risk and ECOG PS (values stated at randomization).

The level of significance to be adopted is described in Section 5.5.

In addition, the two-sided 95% CI for the difference between the responder proportions in the two treatment groups will be provided, using the stratified Newcombe method.

The analysis will be primarily performed in the ITT set (patients for whom no efficacy assessment is available will be analyzed as not having CR) and then in the EE-1 set.

Unstratified analysis will be done for sensitivity purpose by means of likelihood ratio Chi square test.

Logistic regression models will be set up including also demographic characteristics (especially the AML history variables as described in section 7.2) and factors described in section 5.3 as covariates to explore the influence of these variables on CR rate (likelihood ratio test to compare different models and Wald test to evaluate covariates within a model).

Transfusion Independence

For the evaluation of transfusion independence (which is defined as achieving eight weeks or longer with neither red blood cell nor platelet transfusions during the study period), the following transfusions are regarded as “relevant” transfusions:

- Red Blood Cell (RBC) transfusions
- Platelet (PLT) infusions
- Whole Blood infusions

Transfusion independence rate is defined as the proportion of patients who achieve eight weeks or longer with no “relevant” transfusion during the study period.

The period of transfusion independence will be calculated for each patient as the duration (in days) from baseline (Cycle 1 Day 1) to the first “relevant” transfusion during the study period, and then between each subsequent “relevant” transfusion up to the last visit where this information was collected.

If at least one of the durations calculated is greater or equal to 56 days, the patient is regarded as transfusion independent within study period.

The proportion of patients who showed transfusion independence will be summarized by study treatment and transfusion dependence at baseline (patient received any kind of transfusion during the eight weeks prior to baseline).

In addition, the transfusion independence will be calculated separately for each of the relevant transfusions specified above. The proportion of patients who showed transfusion independence from RBC, PLT (whole blood transfusions are included in both categories for the calculations) will be also summarized by treatment.

The proportion of patients who are transfusion independent during study will be compared between the two treatment groups using the same methods as those used for the CR rate analysis including only treatment and stratification factor values documented at randomization. The analysis set will be the ITT set.

All transfusions will be listed.

Complete Remission without Minimal Residual Disease (CR_{MRD-}) rate

The CR_{MRD-} rate is the proportion of patients who achieve a CR with MRD negativity by multi-color flow cytometry, according to the IWG response criteria (Appendix F of the protocol) within the study period. Absence of interceding therapies is requested for considering the response in the analysis (for both CR and MRD negativity).

CR_{MRD-} rate will be analyzed on the ITT and EE-1 sets, using the same methods as those used for the CR rate analysis including only treatment and stratification factors (values stated at randomization). Patients for whom no assessment with multi-color flow cytometry is available at the planned timepoints will be analyzed as not having reached CR_{MRD-}. However patients from sites for which no assessment of MRD was possible due to logistic reasons will be excluded from the ITT/EE-1 sets.

The current definition of the endpoint is applicable also to the patients assessed according to the scheduling given in previous protocol version.

The following rules will be applied.

- A CR should be reported in the Response form.
- A MRD negativity should be reported with a collection date (for blood) greater than or equal to collection date of BM used for declaring CR.
- No progression/relapse/PR/SD should be reported between the above dates of collection.

Cytogenetic Complete Remission (CR_C) rate

The rate of Cytogenetic Complete Remission (CR_C) is defined as the proportion of patients who achieve a reversion to normal karyotype at CR according to the IWG response criteria (Appendix F of the protocol) within the study period. Absence of interceding therapies is requested for considering the response in the analysis.

CR_C rate will be analyzed on the ITT-2 set (as this endpoint applies only to patients with abnormal cytogenetics at enrollment). CR_C rate will be analyzed using the same methods as

those used for the CR rate analysis including only treatment and randomization factors. The endpoint will also be analyzed in EE-2 set.

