- Biomarker analysis (if consent obtained by patient): Peripheral blood samples and/or aspirate bone marrow samples will be collected and stored for potential molecular studies (Section 6.4)

5.1.3 Cycle 1 on Day 1

After confirmation of eligibility, the patient will be randomized to one of the two treatment groups using the IWRS. The following activities are to be performed **before study treatment administration**:

- Assess transfusions of red blood cells or platelets performed during the previous 8 weeks (Section 6.1.2).
- Perform a limited physical examination
- Measure blood pressure and pulse rate –**pre-dose** (sitting or in semi-supine position), body temperature, and weight
- 12-lead ECG measurement in triplicate - **pre-dose**
- Collect concomitant medications and any new medical conditions since the screening visit
- Assess ECOG performance status
- Administer the Quality of Life questionnaire
- Urine pregnancy test for women of childbearing potential – **pre-dose**
- Re-check of all eligibility criteria
- Assessment of adverse events
- Randomization via IWRS: The IWRS will provide the investigator with the kit number stored in the site stock to be dispensed to the patient.
- Treatment administration: The study treatment administration schedule is the following:
 - Pracinostat/placebo administration (see Section 4.2): according to the indication reported on the study kit internal panel, the patient will receive 1 capsule of study drug or matching placebo (week 1, day 1). Patient must begin study treatment within 24 hours after randomization.
 - Azacitidine administration: according to indication reported in Section 4.3.1.2 azacitidine is administered to patient.

Pracinostat/Placebo oral administration is to be taken before administration of azacitidine.

The date and the precise time (hh:mm) of the study drug and Azacitidine administration as well as other information related to the quantity and origin of the Azacitidine vials must be recorded in the source records as well as on the relevant eCRF page for each medication given. The relevant peel-off labels from the study kit and from the Azacitidine commercial packs used for the treatment at this visit will be attached to the drug accountability log (pharmacist or designated responsible).

Activities to be performed **after study drug administration (for all patients EXCEPT those participating in the AZA/pracinostat PK sub-study**. See Section 6.3):

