6.5.2 Secondary Endpoints

6.5.2.1 Morphologic Complete Remission (CR) rate

6.5.2.2 *The CR rate is the proportion of patients who achieve a morphologic CR according to the IWG response criteria ([Appendix F](#)) in the absence of interceding therapies, including salvage treatments and HSCT, within the study period. Transfusion Independence (TI)*

Transfusion independence rate is defined as the proportion of patients who achieve eight weeks or longer with neither red blood cell (RBC) nor platelet (PLT) transfusions during the study period [[Fenaux, 2009](#); [Silverman, 2006](#)].

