9.11 Power and Sample Size Determination

This is an event-driven study. Sample size was computed for a group-sequential design with stopping rules for both futility and superiority (study-wise one-sided alpha level=0.025, power 0.90) with one interim analysis at 67% (2/3) of information and a final analysis. The error spending function is from the Gamma Family, using $\gamma=-3.6$ (similar to O'Brien Fleming) for superiority and $\gamma=-5.5$ (more conservative than O'Brien Fleming) for futility (non-binding). Proportionality of hazards is assumed. Assuming that median OS is 10.0 months in the Group B (placebo + AZA) the aim is to detect, by means of the log-rank test or equivalent, an increase to 14.0 months in Group A (pracinostat + AZA), i.e., a HR of 0.714. A total of 390 events (deaths) allows to meet a power requirement of at least 90% (actually 90.78%) at a study-wise one-sided significance level of 0.025.

Patient accrual is assumed to occur over a 30-month period. Assuming a non-constant accrual rate (100 patients during the first year and the remain patients during the following 1.5 years) and a 3% yearly drop-out rate, and considering that 500 patients will be recruited, it is expected that the post-recruitment follow-up period will take about 18 additional months to reach 390 events for final OS analysis.

Sample size calculations were made using SAS 9.2.

The overall event rate (blinded) will be constantly monitored. Before the expected recruitment end, the observed placebo hazard rate will be derived from the (blinded) overall observed hazard rate at that time, assuming a hazard ratio of 0.714. Based on the computed value the decision to adapt the sample size to enable study end within a reasonable amount of time from the end of recruitment might be taken. This procedure does not introduce bias and no statistical adjustments to preserve the study-wise alpha error are required.

A group-sequential procedure will be applied also to the secondary endpoints, adopting as the error spending function for superiority the Gamma Family, using $\gamma=3.6$. Details on the procedure and power calculation for the secondary endpoints will be provided in the SAP.

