5.5 SIGNIFICANCE LEVEL

The overall significance level for the primary efficacy endpoint is 0.025 (one sided). As an interim analysis according to the O'Brien Fleming function for superiority and the Gamma family function (with $\gamma=-5.4695$ for non-binding futility) will be done after 260 events (2/3 of the total number of events), the respective significance levels are 0.00605 for the interim and 0.02314 for the final analysis. These significance levels will be re-computed at time of analysis based on the real fraction of information available.

Calculations of significance levels and related thresholds were performed by means of SAS PROC SEQDESIGN.

The following table shows probabilities to stop at interim analysis for futility or superiority with the null and alternative hypotheses for the primary endpoint:

Table 1 Probability to stop at Interim Analysis HA as Median OS	10 months	14 months
Gamma spending function $\gamma=-5.4695$ for futility	0.70094	0.01442
O'Brien Fleming for superiority	0.00605	0.58059

The following table shows probabilities of significant results for the first secondary endpoint, according to the chosen hierarchical procedure and assuming no need to consider the correction for multiplicity as 100% of information would be collected (which was the assumption at time of SAP V1). The reference alternative hypothesis is that the difference between treatments in the CR rate is 0.13 (having 0.20 as the rate for the placebo group). Probabilities are corrected by unconditional probability of significant results for the primary endpoint as conditional probability assumes the correlation between endpoints to be known. The obtained results are conservative and represent the lower probability bound assuming no correlation.

Table 2		
Secondary endpoint(s)		
Assumption: 100% information for secondary endpoint at interim analysis is available		
probability of significant results	0.13 rate difference	
	Independent from primary endpoint (i.e. as it was the only endpoint in the study)	Hierarchical procedure *
at Interim Analysis	0.91	0.55
Overall	0.91	0.82

* rounded power for the primary endpoint is 0.90 overall and 0.60 at interim analysis, respectively (median OS = 14 months vs. 10 months)

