However, it is now assumed that not all the patients could be recruited at time of interim look or some of them could not be followed-up for enough time and considering that correlation between the primary endpoint and the secondary endpoints cannot be assumed to be null even if difficult to quantify (no correlation would have justified not correcting for multiplicity), a procedure that manages the multiplicity due to having planned for an interim analysis is needed. The Bonferroni correction (with 0.002 and 0.023 as the partition of the overall alpha level) will be adopted, regardless of the quantity of patients and the time of follow-up. Interpretation of p-values will be based on the hierarchy defined in section 5.4. The family-wise error rate of 0.025 will be adhered to [2, 3].

According to current recruitment rate, 85% of patients on average will have been recruited before the interim analysis time.

The O'Brien Fleming bound for the primary endpoint and Bonferroni criterium for the secondary endpoint(s) will then be adopted, leading to the probability of significant results being as reported in the following table.

Table 3		
Secondary endpoint(s) - probability of significant results at Interim/Final Analysis		
Assumptions: 85% of patients randomized and Bonferroni (0.002, 0.023)		
	0.13 rate difference	
	Independent from primary endpoint (i.e. as it was the only endpoint in the study)	Overall Hierarchical procedure **
Probability of significant results at Interim Analysis	0.56	0.34
Probability of significant results Overall	0.82*	0.74

power for the primary endpoint is rounded to 0.90 overall and 0.60 at interim analysis (median OS = 14 months vs. 10 months)

*assuming 0.6 as the probability to obtain significance at FA given failure at IA (as not all the 85% of patients will have been followed-up for more than 6 months)

** performing test on secondary endpoint also at FA in the case the primary is significant at IA but secondary is not

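### Transfusion independence credits keeping an independent entry state the same as becoming independent, and its confirmatory test leaves out baseline transfusion status: a loss of efficiency and interpretability, not of validity

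*SAP*

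**What the plan says.** Protocol 6.5.2 defines the endpoint as the "proportion of patients who achieve eight weeks or longer with neither red blood cell (RBC) nor platelet (PLT) transfusions during the study period". SAP 8.2 makes this operational. Intervals run from Cycle 1 Day 1 to the first red cell, platelet or whole blood transfusion, then between successive transfusions. The rule is: "If at least one of the durations calculated is greater or equal to 56 days, the patient is regarded as transfusion independent". The analysis set is the full ITT set.

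The test is carried out "using the same methods as those used for the CR rate analysis including only treatment and stratification factor values documented at randomization". For CR, that method is a CMH test stratified by cytogenetic risk and ECOG, with a stratified Newcombe interval.

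Baseline status is available. On Cycle 1 Day 1 the site must "Assess transfusions of red blood cells or platelets performed during the previous 8 weeks" (Protocol 5.1.3). SAP 8.2 summarises the endpoint by treatment and by "transfusion dependence at baseline (patient received any kind of transfusion during the eight weeks prior to baseline"). That is its only stated use: it is absent from the test, from the subgroups in SAP 5.3 and from the single transfusion independence row in SAP Section 13.

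Under SAP 5.4, transfusion independence is tested only if OS and then CR are significant. If it fails, CR without MRD and cytogenetic CR become exploratory.

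**The concern.** Consider a patient untransfused for eight weeks before Day 1, untransfused for 56 days on study, and transfused weekly afterwards. This patient is a responder, exactly like one who arrives heavily transfused and becomes independent. The first has kept an entry state for a time and the second has gained something, so the overall rate mixes maintenance with conversion.

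If status at entry predicts the outcome, leaving it out of the test puts explainable between-patient variation into the error term. The cost falls on an endpoint that gates two others, and the covariate is already collected. The plan follows a different principle for cytogenetic CR, which it limits to patients with abnormal cytogenetics at enrollment because the endpoint applies only to them.

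**Working it through.** **Inputs from the documents.** 500 patients ("considering that 500 patients will be recruited", Protocol 9.11) randomised 1:1, so 250 per arm. For the significance level of the secondary endpoints: "The Bonferroni correction (with 0.002 and 0.023 as the partition of the overall alpha level) will be adopted" (SAP 5.5). The one-sided final level of 0.023 is used here.

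**Inputs that must be assumed.** The documents give no share independent at entry, no transfusion independence rate and no effect on it. I take a share f of 30, 40 or 50%. Control rates (entered independent / entered dependent) are 75%/30%, 60%/35% or 55%/35%. There are two effect patterns: +9 points in patients who entered independent and +12 in those who entered dependent, or +13 in dependent patients only.

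**Nearest stated figure.** SAP Table 2 gives power 0.91 for CR at 0.20 versus 0.33. The pooled normal approximation gives 0.911 with 250 per arm and one-sided 0.025. Table 3's 0.56 at the interim (85% of patients, 212.5 per arm, level 0.002) comes out at 0.564. The method matches the sponsor's.

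**Formula.** Power = Φ[(Δ − 1.995·s0)/s1].
- Without baseline status: p0 and p1 are the pooled arm rates with mean p̄; s0² = 2p̄(1−p̄)/n; s1² = [p0(1−p0)+p1(1−p1)]/n.
- With baseline status: Δ, s0² and s1² are averages of the same quantities within each baseline group, weighted f and 1−f.

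**Worked case**, f = 40%, 75%/30%, benefit in both groups. p0 = 0.4×0.75+0.6×0.30 = 0.480; p1 = 0.4×0.84+0.6×0.42 = 0.588; Δ = 0.108.
- Without baseline status: s0 = 0.0446, s1 = 0.0444, power 0.67.
- With it: s0 = 0.0403, s1 = 0.0400, power 0.75.

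**All cases** (power without → with baseline status, for f = 30 / 40 / 50%):

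| Control rates | Benefit in both groups | Benefit in dependent patients only | Gain, points |
|---|---|---|---|
| 75%/30% | 0.69→0.76 / 0.67→0.75 / 0.65→0.74 | 0.52→0.57 / 0.40→0.46 / 0.30→0.34 | about 4-10 |
| 60%/35% | 0.69→0.71 / 0.66→0.69 / 0.64→0.67 | 0.52→0.53 / 0.40→0.41 / 0.29→0.30 | about 1-2.5 |
| 55%/35% | 0.69→0.70 / 0.66→0.68 / 0.64→0.65 | 0.52→0.53 / 0.40→0.41 / 0.29→0.30 | about 0.5-1.5 |

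The cytogenetic and ECOG strata are left out of both columns because nothing is known of how they relate to transfusion need. Any such relation would shrink the gain.

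**Variance removed.** 1 − [f·pI(1−pI)+(1−f)·pD(1−pD)]/[p(1−p)], where pI and pD are the control rates in the two baseline groups and p is the pooled control rate. This is 17-20% at 75%/30%, 5-6% at 60%/35% and about 4% at 55%/35%.

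**Interpretation.** The share of control responders who entered independent is f·pI/p. At 75%/30% this is 0.225/0.435 = 52%, 0.300/0.480 = 63% and 0.375/0.525 = 71%. A +13 point effect confined to dependent patients shrinks in the ITT set to 13×(1−f) = 9.1, 7.8 and 6.5 points. Stratifying does not undo that dilution; it only reduces the noise around it.

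**Type I error.** In 200,000 simulated null trials (40% independent at entry, rates 75%/20%, nominal 0.023), the test without baseline status rejected in 0.0234.

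**The case against.** The strongest reply is that the endpoint is legitimate as written. A reader might infer that patients who enter independent are counted automatically. They are not: they too need 56 transfusion-free days on study, on a myelosuppressive regimen. Protocol 1.3 reports Grade ≥3 thrombocytopenia in 46% and anemia in 30% of the Phase II patients. Staying transfusion-free on that regimen is an on-treatment outcome, and conversion alone would be a different estimand. This stands, and it is why the fix keeps the ITT set and the responder rule. Restricting the test to dependent patients would also cost power if treatment helps maintenance.

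A reader might also infer a biased or invalid test. The documents do not support that. Randomisation balances baseline status in expectation, and chance imbalance is already covered by the error rate.

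Nor do the documents support a large, fixed cost in sample size. A figure such as 21-26% more patients follows only from assuming 75%/30%; nothing in the plan shows that baseline status is that strong a predictor.

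Part of the remedy is already planned. The descriptive table by baseline dependence will show both rates per arm. SAP 5.2 and Section 13 let the blind data review consider further covariates and add sensitivity or subgroup analyses, and Protocol 9.7.4 foresees subgroups by baseline characteristics. None of this commits to the adjusted test or to between-group intervals.

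Finally, timing. SAP Section 11 says this version contains changes decided after the interim results were unblinded, and SAP 8.1.2 makes all secondary tests exploratory if the study stops at the interim. Both limit what can still be changed and what is at stake.

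**Conclusion.** The point holds as one of efficiency and interpretation. The responder rule gives equal credit for maintaining and for gaining independence, and the confirmatory test leaves out a baseline covariate that the trial collects and already tabulates. The direction of the power loss is secure whenever baseline status predicts the outcome; its size is not. With 250 per arm, one-sided 0.023 and 30-50% independent at entry, the gain is about 4-10 points under a strong baseline contrast (75%/30%) and about 0.5-2.5 points under weaker ones (60%/35%, 55%/35%). These figures do not allow for the existing strata. The consequence is bounded further because the endpoint is tested only after OS and CR succeed. It is a cheap improvement worth making, not a flaw in the trial's error control.

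**What to change.** - In SAP 8.2 and Section 13, add baseline transfusion dependence as a further stratum in the CMH test and the stratified Newcombe interval for transfusion independence.
- Define it over the eight weeks before Cycle 1 Day 1, counting the same red cell, platelet and whole blood transfusions as on study. At present the baseline definition takes any kind of transfusion while the on-study rule counts only these relevant ones. The Day 1 look-back in Protocol 5.1.3 names only red cells and platelets, so check that whole blood is captured.
- Where the interim results are already unblinded and the confirmatory test can no longer be changed credibly, leave that test alone and run the stratified one as a labelled sensitivity analysis.
- Extend the planned table to give the conversion rate (dependent to independent) and the maintenance rate (independent to independent), each with the between-group difference and confidence interval.

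The cost is SAP wording and some programming, with no new assessments apart from the whole blood check. The downside is eight strata instead of four, a few of them sparse; the CMH test pools across them.
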